5.0 Inclusion/Exclusion Criteria

5.1 Inclusion Criteria. Consecutive patients will be eligible for inclusion in the SCOPE trial if they are:adult patients (≥ 18 years old) scheduled for one of the following abdominal operations with intent to provide cure or durable oncologic control of malignancy:

- 1) Total or partial gastrectomy requiring anastomosis
- 2) Total or partial pancreatectomy
- 3) Partial hepatectomy
- 4) Colectomy or proctectomy if one of the following 3 conditions is also met:
 - i) patient age is 65 years or older
 - ii) disease is metastatic
 - iii) disease is locally invasive requiring extensive resection
- 5) Radical cystectomy
- 6) Pelvic exenteration
- 7) Abdominal debulking for ovarian or endometrial carcinoma
- 8) Cytoreductive surgery and hyperthermic intraperitoneal chemotherapy

5.2 Exclusion Criteria. Patients will be excluded (i.e., not consented) for any of the following reasons:

- [1] Non-English speaking patient
- [2] Residence >150 miles away from Vanderbilt and do not visit the Nashville area regularly
- [3] No telephone or otherwise unwilling/unable to complete follow-ups
- [4] Prisoner
- [5] Current enrollment in a study that does not allow co-enrollment or that uses a non-pharmacologic, non-procedural intervention directed at surgical or cancer care.
- [6] Deaf
- [7] Severe prior cognitive or neurodegenerative disorder that prevents a patient from living independently at baseline
- [8] Inability to obtain informed consent from patient meeting all inclusion criteria for the following reasons:
 - (a) Attending surgeon refusal
 - (b) Patient refusal
 - (c) Period of time between screening patient and time of operation does not allow preoperative outpatient palliative care visit.
- [9] Currently participating in palliative care or seeing a palliative care provider.

6.0 Enrollment/Randomization

6.1. Screening and Obtaining Informed Consent. Patients will be identified at their clinic visits to a surgeon to schedule a resection of an eligible malignancy. Study staff will determine eligibility. When an eligible patient is identified (i.e., inclusion criteria are met and no exclusion criteria are present), informed consent will be pursued. Additionally, the patient will identify a caregiver who will be the subject for caregiver evaluation and will be the contact person in later phases of the study if the patient is unable to respond for him or herself. In some cases, the main caregiver may change due to various circumstances and a new caregiver will be contacted. Patient will be randomized and assigned via randomization to the Intervention Group or the Control Group.

To maintain group balance among types of malignancy, a critical determinant of outcome, the treatment group allocation will be specified by stratified randomization. We will randomize patients meeting all eligibility requirements in a 1:1 ratio to early PCC or standard of care using a computer-generated randomization scheme using a permuted block design, stratified by type of cancer. The randomization scheme will be created by the trial's primary biostatistician and be directly uploaded into REDCap's randomization module. In rare cases some patients may be enrolled into trial but not randomized for uncontrollable reasons such as a surgery date is talked about with patient with the expectation that surgery may not occur due to lack of response to a therapy. Some surgeons have tight windows of time scheduling the patient a few days after a scan which gives little room to meet with patient to consent and complete pre-surgery interventions. It will be rare (<10% of patients enrolled) that a patient is consented without randomization but the study team wants the option to connect with these patients when it is most convenient for them. The goal is to have 236 randomized patients with the expectation that more than 236 patients may be enrolled/consented to get to a total of 236 patients randomized.

6.2 Blinding. The post-op assessments of patients will be completed by a masked outcome assessor who is not aware of randomization assignments of patients. The assessors will be trained to avoid discussing assignment during their interactions with subjects.

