4.2 Efficacy Endpoints

4.2.1 Primary Endpoint. The trial's primary endpoint will be score on the FACT-G TOI at 90 days post-operatively (controlling for baseline score).

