10.0 Statistical Considerations

10.1 Power analyses and sample size calculations. Previous studies have demonstrated a moderate effect (effect size ~0.4) of early palliative care on TOI, which is the primary outcome of the SCOPE trial. Assuming a type I error rate of 5% and a common standard deviation of 18.1 in the FACT-G TOI score in each group, 98 subjects in each group at 90 days (total N=196) would provide the study with at least 80% power to detect a change of 7.28 points (an effect size of 0.4) for TOI, the primary outcome of the SCOPE trial. Assuming 15% loss to follow-up at 90 days, enrolling 118 patients per group (total N=236) would provide this level of power. The study will not be powered to meet the secondary and exploratory outcomes.

The demographic and clinical characteristics of patients will be described using descriptive statistics. For continuous variables, median and interquartile range will be used while categorical variables will be described using frequency (percentage).

To examine the unadjusted effect of treatment on the primary end-point for the SCOPE trial, 90-day functional status as measured by the FACT-G TOI, we will use the Wilcoxon rank-sum test. In addition to unadjusted analyses, we will also perform multivariable regression to adjust for a priori-selected risk factors for outcomes, including age, frailty, cancer type, insurance status, education level, and degree of religious involvement. We will choose the type of multiple regression by carefully examining the distribution of the data. In the case of non-normally distributed outcomes, we will use a multivariable proportional odds regression model. To determine the unadjusted effect of early PCC on hospital length of stay, survival, and other time-to event outcomes, the cumulative incidence probability of these outcomes will be estimated via the Kaplan-Meier product limit method, and the log-rank test will be used to compare groups. Cox proportional hazards regression will be used to analyze the adjusted effect of PCC on time-to-event outcomes, with censoring as appropriate. To evaluate the unadjusted association between early PCC and receipt of intensive life-prolonging therapy in the last two weeks of life,

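### The planned analyses of 90-day TOI do not together use the stratification factor and the baseline score, and neither is named as primary

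*Combined protocol and SAP*

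**What the plan says.** **Design.** Section 6.1 specifies a "computer-generated randomization scheme using a permuted block design, stratified by type of cancer", with 1:1 allocation. The reason it gives is "To maintain group balance among types of malignancy, a critical determinant of outcome". The number of strata and the block size are not stated.

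**Endpoint.** Section 4.2.1 defines the primary endpoint as "score on the FACT-G TOI at 90 days post-operatively (controlling for baseline score"). Aim 1 in section 1.0 also defines it as controlled for baseline.

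**Analysis.** For the unadjusted effect on the primary endpoint, section 10.1 says: "90-day functional status as measured by the FACT-G TOI, we will use the Wilcoxon rank-sum test". No strata are mentioned. A regression on prespecified risk factors is planned as well, and its covariates are given as "including age, frailty, cancer type, insurance status, education level, and degree of religious involvement". The type of regression is to be chosen after examining the distribution of the data, with a proportional odds model for non-normal outcomes. Baseline TOI is not among the listed covariates. For time-to-event outcomes, section 10.1 plans a log-rank test, again without strata, and an adjusted Cox model. Nothing in section 10.1 ranks the unadjusted analysis above the adjusted one or the reverse.

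**The concern.** Blocked randomisation within cancer type forces the arms to be nearly balanced on cancer type. Differences in outcome between cancer types then contribute almost nothing to the treatment contrast. A plain Wilcoxon test still counts those differences in its variance. If cancer type predicts TOI, as the protocol implies when it explains the stratification, the test's null variance is too large: it rejects less often than 5% under the null and misses some true effects that a stratified analysis would detect.

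The baseline score raises a related problem. An endpoint defined as controlling for baseline is not what a Wilcoxon test on 90-day scores examines, and the regression as listed does not supply the control either. At stake are precision, and clarity about which result answers the trial's question. The validity of the type I error is not at stake.

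**Working it through.** **Inputs from section 10.1.** Difference 7.28 points, SD 18.1, alpha 0.05 (sidedness not stated), 98 evaluable per arm, 80% power, 15% loss, 118 enrolled per arm.

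**Reproducing the plan's figures.** SE = 18.1 × √(2/98) = 2.586, and 7.28/2.586 = 2.816. Two-sided power = Φ(2.816 − 1.96) = Φ(0.856) = 0.804, so 98 per arm reproduces. A one-sided test would need 77, so the plan is evidently two-sided. Allowing for loss, 98/0.85 gives 116 per arm against 118 stated, and 118 × 0.85 = 100.3 evaluable per arm. The sample size holds.

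**Assumptions not in the documents.** Let ρ be the share of TOI variance explained by cancer type, with total SD held at 18.1. The simulation also assumes 8 unequal strata, blocks of 4, normal data and loss at random.

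**Approximation at 98 per arm.**
- Unstratified test: true alpha = 2[1 − Φ(1.96/√(1−ρ))]; power = Φ((2.816 − 1.96)/√(1−ρ)).
- Stratified test: power = Φ(2.816/√(1−ρ) − 1.96).

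At ρ = 0.10, √(1−ρ) = 0.949. True alpha is 2[1 − Φ(2.066)] = 0.039, unstratified power is Φ(0.902) = 0.816, and stratified power is Φ(1.008) = 0.843.

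| ρ | True alpha, unstratified | Power, unstratified | Power, stratified |
|---|---|---|---|
| 0 | 0.050 | 0.804 | 0.804 |
| 0.05 | 0.044 | 0.810 | 0.823 |
| 0.10 | 0.039 | 0.816 | 0.843 |
| 0.20 | 0.028 | 0.831 | 0.883 |

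**Simulation.** 236 randomised, 15% lost; 8,000 trials under the null and 5,000 under the alternative for each ρ.

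| ρ | Wilcoxon alpha | Power, Wilcoxon | Power, van Elteren | Power, linear model with strata |
|---|---|---|---|---|
| 0 | 0.053 | 0.78 | 0.76 | 0.80 |
| 0.05 | 0.044 | 0.78 | 0.78 | 0.81 |
| 0.10 | 0.040 | 0.81 | 0.82 | 0.85 |
| 0.20 | 0.034 | 0.81 | 0.86 | 0.89 |

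Simulation error is about one power point, and repeat runs gave Wilcoxon alphas of about 0.045, 0.039 and 0.035 at the three non-zero shares. Against a rank model with strata, the power forgone is about 1 to 6 points over ρ = 0.05 to 0.20. The linear model's lead also includes about 2 points that have nothing to do with strata (0.80 against 0.78 at ρ = 0), because the Wilcoxon test has efficiency 3/π when data are normal.

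**Adding baseline TOI.** Assume a correlation of 0.5 with 90-day TOI, within strata. The residual variance is multiplied by 1 − 0.25 = 0.75. With ρ = 0, power = Φ(2.816/√0.75 − 1.96) = Φ(1.29) = 0.90. With ρ = 0.10, the factor is 0.9 × 0.75 = 0.675, and power = Φ(2.816/√0.675 − 1.96) = Φ(1.47) = 0.93.

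**The case against.** The strongest reply is that section 10.1 already adjusts for cancer type. The regression lists it, a proportional odds form is specified for non-normal outcomes, and the log-rank test is paired with an adjusted Cox model. This stands in large part. What remains missing is baseline TOI in the covariate list, a regression form fixed in advance, and a statement of which analysis is primary.

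A second reply is that the gain from the strata is small and rests on figures the documents do not give. This also stands. The protocol's remark about the importance of malignancy type does not say which outcome is meant and gives no variance share for TOI. At a 5% share, van Elteren gains nothing. At zero it costs a point or two, because small strata waste information.

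Third, no calculation here supports the log-rank change, and section 10.1 says that the study is not powered for secondary and exploratory outcomes. Stratifying that test is a matter of consistency with the design, not a quantified gain.

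A reader might go further and infer that the Wilcoxon test is the designated primary analysis, since it comes first and is the only test fixed by name for this endpoint. The text calls it only the unadjusted analysis, so that inference is not supported.

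**Conclusion.** The point holds as a low-cost improvement in precision and clarity. No single planned analysis, as listed, uses both cancer type and baseline TOI, and none is designated as primary. If cancer type explains 5% to 20% of TOI variance, the unstratified Wilcoxon test runs at a true alpha of about 0.045 to 0.034. It forgoes about 0 to 5 power points against van Elteren, or about 1 to 6 against a rank model with strata. These figures depend on the assumed share, 8 unequal strata, blocks of 4, normal data and random loss. The larger gain comes from baseline TOI: about 90% power or more under an assumed correlation of 0.5.

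Two stronger readings should be avoided. Type I error is not inflated; under prognostic strata it falls below 5%. Nor do the strata erode the planned 80%: unstratified power rises slightly with the variance share, from 0.804 at zero to 0.831 at 0.20 by approximation. The simulated 0.78 at zero share reflects Wilcoxon efficiency under normal data (about 0.786 at 98 per arm), which is a separate matter.

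**What to change.** In section 10.1, name one primary analysis of 90-day TOI: a proportional odds model (or a linear model, if that choice is fixed before unblinding) with treatment, cancer-type randomisation stratum and baseline TOI. State a rule, also fixed before unblinding, for pooling very small strata. Keep the Wilcoxon test as a sensitivity analysis. Van Elteren is not the preferred replacement, because it can lose a point or two when cancer type is weakly prognostic, and it does not use baseline. Stratify the log-rank test by cancer type.

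The model fits the plan's own limit of one parameter per ten effective observations. With 8 strata assumed and baseline entered linearly it has 1 + 7 + 1 = 9 treatment and covariate parameters, against about 196/10 = 19 allowed. The cost is wording only: the stratum is recorded at randomisation and baseline quality of life is already collected, so no patients, visits or data items are added.

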7.0 Study Procedures

7.1 Enrollment. After informed consent is obtained, on the day of enrollment baseline demographic, clinical, and psychometric data will be collected on all consented subjects if feasible. If baseline information is not obtained on consent day, it will be completed as soon as possible and always before scheduled operation date.

The following procedure will be conducted:

A **baseline function assessment** form will ascertain important information about the patient's baseline functional status, including history of depression and anxiety. Quality of life will be measured.

7.2 Intervention Trial. The Intervention Trial Phase will comprise of the Pre-operative Phase, In-Patient Phase, and the Long-Term Follow-up Treatment Phase. Patients in the control group will receive routine care for their malignancy and can receive palliative care consultation at the discretion of their providers. Patients assigned to the intervention group will be immediately scheduled for a preoperative outpatient palliative care consultation by a physician or

nurse practitioner on the Vanderbilt palliative care team. This encounter will focus on advance care planning, helping the patient articulate goals of care, and addressing any symptoms the patient is experiencing. If the patient is unable to come for the scheduled in-person consultation, a provider will contact them by phone to provide a phone consultation. Intervention patients will be compensated with a \$50 gift card or check for coming to the pre-operative in person palliative care visit. Patients in the intervention group will also receive an inpatient palliative care consultation at least twice weekly during post-op hospitalization focusing on pain and symptom management and addressing any psychosocial distress around the operation. While inpatients, the palliative care team will follow these patients at the discretion of the palliative care provider.

After discharge the intervention group patients will have three outpatient follow-up contacts (in person visit or phone call) with a palliative care provider in the first 90 days post-operatively to address any symptoms and to continue addressing goals of care and any psychosocial distress. Patients will be compensated with a \$50 gift card or check if they come to at least one in person post-operative palliative care clinic visit. From that point, the patient will have continued follow-up appointments in the outpatient palliative care clinic at a frequency at the discretion of the palliative care provider, with recommended appointment frequency of at least every 3 months. A palliative care visit is planned on every subsequent inpatient admission at Vanderbilt during the three-year study period. If an intervention patient is not able to come to a scheduled outpatient palliative care clinic visit, a phone call between the provider and the patient will be scheduled instead.

Data Timeline

Construct	Scale	Baseline	30 Days	60 Days	90 Days	180 Days	Biannually up to the end of 3 years	Post-Mortem (Final)
Demographics								
Cancer Type								
Operation								
Comorbidities	Charlson Comorbidity Index							
Frailty	Risk Analysis Index							
Cognitive Impairment	AD-8							
ASA Class								
Employment								
Religiosity/Spirituality	DUREL							
Functional Status	FACT-G TOI							
Functional Status	Karnofsky PS							
Quality of Life	FACT-G							
Anxiety	PROMIS Anxiety 6							
Depression	PROMIS Depression 6							
Fatigue	PROMIS Fatigue-Short Form 6a							
Hospital Satisfaction	HCAHPS Question 21							
PTSD	PTSD Checklist-Civilian Version							
Post-traumatic growth	Post-traumatic Growth Inventory							
Initiation of Adjuvant Rx								
ER Visits w/o admission								
Unplanned hospital admissions								
Hospital/Facility LOS								

Caregiver Burden	Zarit Burden Interview				Yellow	Blue	Yellow	
Size of Lifespan	Life Space Assessment Questionnaire				Yellow	Blue	Yellow	
Long term care residence					Yellow	Blue	Yellow	
Date of Death								Blue
Date of Last Chemo								Blue
Hospice Admission Date								Blue
Hospice LOS								Blue
Quality of Death	FATE-S							Blue
Location of Death								Blue

*Abbreviations (alphabetical): **AD8**- Alzheimer Disease, **ASA**-American Society of Anesthesiologists, **DUREL**- Duke University Religion Index , **ER** – Emergency Room, **FACT-G**-Functional Assessment of Cancer Therapy - General, **TOI**-Trial Outcome Index, **FATE-S**-Family Assessment of Treatment at End of Life Short Form, **HCAHPS**-Hospital Consumer Assessment of Healthcare Providers and Systems , **LOS**-Length of Stay, **PROMIS**-Patient-Reported Outcomes Measurement Information System , **PS**-Performance Status , **PTSD**- Post Traumatic Stress Disorder, **Rx**- Prescription

7.2.2 Interventional Trial: Follow-up Phase. We will evaluate outcomes among survivors, approximately **90 days** after operation. The follow-up team will be blinded to patient assignment and will be instructed to avoid having patients reveal treatment group. Under the direction of the Vanderbilt Coordinating Center's lead neuropsychologist, trained study personnel will assess patients using the following validated telephone assessments:

- [1] Functional Assessment of Cancer Therapy-General (FACT-G) Trial Outcome Index (TOI) assessing functional status.
- [2] Karnofsky performance status assessing functional status.
- [3] FACT-G assessing Quality of Life
- [4] PROMIS Anxiety-6 assessment
- [5] PROMIS Depression-6 assessment
- [6] HCAHPS Question 21 assessment of satisfaction with hospital stay.
- [7] Days alive at home without an Emergency Room (ER) visit
- [8] Initiation of appropriate adjuvant therapy

At approximately 30, 60, and 90 days after the operation, study subjects will be contacted by the research personnel who will inquire about hospitalizations and ER visits and whether patients have initiated chemotherapy or radiotherapy since the operation; these data will be supplemented and corroborated by searches of the VUMC electronic medical record. Because adjuvant therapy is not the optimal therapeutic approach in all patients with these malignancies (some for instance, may require neo-adjuvant therapy that obviates adjuvant therapy), the medical records of all subjects will be examined by an oncologist to determine whether adjuvant therapy would be recommended based on any preoperative treatment and the results of the operation, assuming that the patient's functional status would allow it. The initiation of adjuvant therapy would then

be an outcome for this subgroup of patients. There is also one small subgroup of patients that will have fatigue examined closer at baseline and 30 days after the operation.

At the 90 day assessment the assessors will administer the psychometric instruments listed above to access the 90 day outcomes. Patients who cannot be reached by phone will have hard copy assessments mailed to them and/or electronic versions sent by e-mail with links to the instruments in REDCap.

We will evaluate long-term outcomes among survivors, approximately **180 days** after operation.

- [1] PTSD Checklist-Civilian Version
- [2] FACT G TOI and Karnofsky Performance Status
- [3] Life Space Assessment Questionnaire
- [4] FACT-G
- [5] Trend in employment
- [6] Zarit Burden Interview
- [7] Trend in long-term care residence
- [8] Overall Survival
- [9] Trend in hospital admissions and in ER visits

At approximately 180 days after the operation, the outcomes assessor will again contact the subjects and will inquire about hospital admissions, ER visits, the patient's employment status (full-time, part-time, none) and whether the patient still lives at home or in a long-term care facility. At this time point, instruments to evaluate PTSD, post-traumatic growth, functional status, and quality of life will be administered. Additionally, the assessor will administer the Zarit Burden instrument to the caregiver. At approximately every 6-months thereafter patients and/or caregivers will be contacted, and functional status, life-space, quality of life, employment, long-term facility residence, hospital admissions, and ER visits along with caregiver burden will be assessed. Follow-up will continue for three years. Information about survival will be monitored by periodic surveillance of the medical record for indication of patient deaths as well as by newspaper searches of obituaries. If a scheduled 6-month contact occurs for a patient of whose death the study personnel were unaware, information about date of death will be obtained from the patient's caregiver.

When it is determined that a subject has died, the study personnel will contact the subject's designated caregiver to determine the end of life care utilization: whether and when the patient enrolled in hospice, when the patient's last dose of chemotherapy occurred, hospital admissions

and ER visits in the last month of life, and where the patient died. Additionally, a quality of death and dying survey will be administered to the caregiver

7.3.1 Long-term Follow-Up Patient Retention Plan. In order to maximize full participation of the randomized patients, the Long-Term Follow-Up Committee will rely on strategies refined over the past 15 years to produce a Follow-Up assessment rate of >85%. Study personnel will be instructed to obtain as much contact information as possible at time of enrollment (e.g. multiple phone numbers, mailing addresses, discharge destination etc.). The Neuropsychology Coordinator will perform the following interventions to maintain >85% Follow-Up assessment rates:

- [1] A periodic phone call or letter will serve as an additional reminder of study participation.
- [2] Weekly meetings will be conducted with study staff to evaluate the status of follow-up evaluations, with a particular focus on devising and implementing effective strategies to reach patients who may be difficult to contact. In rare situations, home visits may be conducted to help complete assessments.
- [3] Participants will be compensated a \$50 gift card or check after they complete the 90 day phone assessment.
- [4] Participants may be contacted by SMS text messaging to arrange times to perform assessments or to remind participants to complete electronic versions of assessments. When contacting participants by text, study staff will identify themselves in a message with no PHI and then ask participants to confirm their identity before communicating any potentially identifiable information.

7.4 Data Collection/Case Report Form Details. During all study phases, all data will be entered into electronic case report forms (eCRFs) in a secured password-protected database. Copyrighted forms will be used when required. This study will utilize REDCap for data collection, transmission and storage. REDCap (Research Electronic Data Capture) is a secure, web-based application for building and managing online databases. Vanderbilt University, with collaboration from a consortium of institutional partners, including the Vanderbilt Institute for Clinical and Translation Research (VICTR) Informatics Core, developed and manages a software toolset and workflow methodology for electronic collection and management of research and clinical trial data. All study data will be entered via a password protected, study unique REDCap database website. REDCap servers are housed in a local data center at Vanderbilt and all web-based information transmission is encrypted. REDCap was developed specifically around HIPAA-Security guidelines and is recommended by both the Vanderbilt University Privacy Office and Institutional Review Board. REDCap has been disseminated for use locally at other institutions and currently supports > 140 academic/non-profit consortium partners and 11,000 research end-users (www.project-redcap.org)

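### Section 7.1 allows a late baseline FACT-G TOI to be taken after randomisation, even after the preoperative palliative care visit, so a baseline-adjusted analysis of the primary endpoint could be biased

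*Combined protocol and SAP*

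**What the plan says.** All references are to the combined protocol and SAP.

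- **Timing of baseline (7.1).** The default is collection at enrolment: "on the day of enrollment baseline demographic, clinical, and psychometric data will be collected on all consented subjects if feasible". For the remainder: "If baseline information is not obtained on consent day, it will be completed as soon as possible and always before scheduled operation date".
- **Randomisation (6.1).** After describing consent and the naming of a caregiver, the section says: "Patient will be randomized and assigned via randomization to the Intervention Group or the Control Group". A completed baseline is not named as a precondition.
- **Start of the intervention (7.2).** "Patients assigned to the intervention group will be immediately scheduled for a preoperative outpatient palliative care consultation". The content of that visit includes "addressing any symptoms the patient is experiencing", along with advance care planning and goals of care. It can be held by phone.
- **Primary endpoint (4.2.1; also Aim 1).** "score on the FACT-G TOI at 90 days post-operatively (controlling for baseline score".
- **Masking (6.2).** "The post-op assessments of patients will be completed by a masked outcome assessor who is not aware of randomization assignments of patients". Nothing is said about who takes the baseline.
- **Schedule of events (7.5).** The baseline function assessment sits under Enrollment, and the first palliative care visit under the Pre-operative Phase.
- **Analysis (10.1).** For the unadjusted comparison of "90-day functional status as measured by the FACT-G TOI, we will use the Wilcoxon rank-sum test". The covariates named for the adjusted model do not include baseline TOI, although the list is not worded as exhaustive.

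**The concern.** A baseline covariate is safe to adjust for because treatment cannot have affected it. Section 7.1 does not secure that. Its only fixed limit on a late baseline is the operation, and the first part of the intervention falls inside the window that is still open. A patient could be consented, randomised, seen by palliative care and only then given the baseline questionnaire, without any departure from the protocol.

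The visit deals with symptoms, so it could plausibly change a physical and functional score. Early exposure would be almost confined to the intervention arm: section 12.2 expects almost no control patients to receive palliative care that early. A questionnaire answered after assignment but before the visit is also open to the patient's knowledge of the arm, since only post-operative assessments are described as masked.

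At stake is the treatment estimate from any analysis of 90-day TOI that controls for baseline. Part of the treatment's effect could be removed by the adjustment, or an early fall in scores could be credited to the treatment as benefit. If the dates are not compared, the analysis would not reveal either.

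Late baselines are foreseeable. Section 6.1 acknowledges that some surgeons' scheduling leaves little time for consent and the preoperative steps. Exclusion 8(c) in section 5.2 protects time for the palliative care visit but not for the baseline.

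**Working it through.** **1. The plan's own figure.** Section 10.1 gives a difference of 7.28 points, SD 18.1, type I error 5% and power 80%. Taking the test as two-sided:

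n per group = 2 × [18.1 × (1.960 + 0.842) / 7.28]² = 97.04, rounded up to 98.

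Power at 98 per group is 80.4%. Allowing for 15% loss, 98 / 0.85 = 115.3, so 116 per group; the plan enrols 118. The sample size reproduces and is not in dispute.

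**2. Formula for the bias.** Let ρ be the slope of 90-day TOI on baseline (equal to the correlation if the SDs are equal), f the share of intervention baselines taken after the visit, and d the mean shift the visit causes in those scores. The adjusted estimate is the difference in 90-day means minus ρ times the difference in baseline means. Late collection adds f × d to the intervention baseline mean, so

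bias = −ρ × f × d.

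The documents give none of ρ, f or d. All values below are assumptions. The shift of 3.64 is half of 7.28.

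**3. Results at ρ = 0.5.** The residual SD is 18.1 × √(1 − 0.25) = 15.7, with 98 per group.

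| Share late (f) | Shift (d) | Bias | % of 7.28 | Expected estimate | Power |
|---|---|---|---|---|---|
| 0 | – | 0 | 0 | 7.28 | 90.2% |
| 10% | 3.64 | −0.18 | 2.5% | 7.10 | 88.7% |
| 25% | 3.64 | −0.46 | 6.2% | 6.83 | 86.2% |
| 50% | 3.64 | −0.91 | 12.5% | 6.37 | 81.2% |

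Example: 0.5 × 0.25 × 3.64 = 0.455.

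A simulation with 2,000 runs per case agreed closely. With no late baselines it gave a mean estimate of 7.25 and power of 89.2%. At 25% late it gave 6.84 and 86.4%; at 50% late, 6.29 and 79.4%.

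**4. Range.** With ρ from 0.3 to 0.7, f from 10% to 50% and d from 2 to 3.64, the bias runs from 0.3 × 0.10 × 2 = 0.06 points (about 1%) to 0.7 × 0.50 × 3.64 = 1.27 points (about 18%).

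**5. Direction.** If the visit lowers scores, for example through distress after discussing goals of care, d is negative. With d = −3.64 and ρ = 0.5, the estimate becomes 7.28 + 0.46 = 7.74 at 25% late, and 7.28 + 0.91 = 8.19 at 50% late. Benefit would then be overstated.

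**6. Analyses reached.** The Wilcoxon test in 10.1 has no baseline term, so its bias from this source is zero. The exposure comes through the endpoint definition in 4.2.1 and Aim 1.

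**The case against.** The strongest reply is that the plan already shows the right order. Consent-day collection is the default, late cases are to be completed promptly, and the schedule in 7.5 places baseline in an earlier phase than the first visit. A post-visit baseline needs a missed consent-day collection, randomisation regardless, a visit held, and only then the questionnaire. Section 6.1 is silent on randomising without a baseline; it does not say that this will happen. All of this stands as an argument that the frequency may be low. It does not close the gap, because 7.5 assigns activities to phases while 7.1 expressly permits later collection up to the operation.

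Four stronger readings are tempting, and the documents do not support them.

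- *The primary comparison is biased towards no difference.* The direction depends on an early benefit that the documents do not establish. The unadjusted test is untouched, and baseline TOI is not among the covariates named in 10.1. That mismatch with 4.2.1 is a separate point to reconcile.
- *The trial loses its planned power.* The plan claims 80% for an unadjusted comparison. The 90% starting value comes from the assumed correlation of 0.5, and the cases tabulated above stay at about 80% or more. A clear shortfall (68.4%) appears with half the intervention baselines late and a shift of the full 7.28 points. That would have one preoperative visit deliver the whole 90-day design effect.
- *Every outcome is affected.* Section 4.2.2 lists 90-day FACT-G without baseline control. Other measures are exposed only if they are analysed with a baseline term.
- *The problem must have occurred.* Nothing in the documents shows how many baselines were late.

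**Conclusion.** The concern holds as a gap in a stated timing rule: the plan permits a baseline TOI taken after assignment or after the first palliative care visit, and defines its primary endpoint as controlled for that score. The textual point needs no assumption.

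The size does. For a slope of 0.5, 25% to 50% late and an early shift of 3.64 points, the bias is about 0.5 to 0.9 points, or 6% to 12.5% of 7.28. It shrinks to near zero if late baselines are rare, and its sign follows the sign of the shift. It is confined to analyses that adjust for baseline. This should be fixed, because it touches the primary endpoint and the remedy is cheap. The evidence does not support calling the primary result invalid.

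**What to change.** **Going forward.** In 7.1, require the baseline FACT-G and the other baseline patient-reported instruments to be completed before randomisation, by phone if needed. Repeat the requirement in 6.1, and make completion a precondition for opening the REDCap randomisation module. Section 11.0 describes paper forms for quality of life, so completion must be recorded in REDCap before the module opens.

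**Patients already randomised.** Tabulate the dates of baseline, randomisation and first palliative care visit by arm, and report how many baselines were late. Add a sensitivity analysis that treats every post-randomisation baseline as missing, in both arms, and imputes it from pre-randomisation data without using arm. Setting aside only post-visit baselines would create missing data almost entirely in the intervention arm, and would leave in place those answered with knowledge of assignment.

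**Cost.** Protocol wording, one database gate, a table and one sensitivity analysis. The sample size does not change. Randomisation would be slightly delayed for a few patients. That matters most where the preoperative window is tight, since delay could eat into the time for the preoperative visit; phone completion limits this.
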